### **Control**

Control subjects will receive usual care, managed by the treating physician(s).

### **Data Analysis & Statistical Considerations**

Sample size calculation was performed, assuming a hypothesized increase in P:F ratio of +25 in the intervention group, no change in P:F ratio in the control group, and standard deviation of 30 in both groups. With these assumptions, for statistical power of 80%, a sample size of 46 subjects will be required. With an expected dropout rate of 10%, a sample size of 50 subjects will be necessary to complete the study.

Groups will be analyzed by intention to treat. Per-protocol analyses will also be performed.

Descriptive statistics will be reported for the overall subject population, and for the two groups.

The primary outcome of intra-subject change in P:F ratio before and after using the device will be analyzed with a paired student's t-test. The absolute change and percent change in P:F ratio will be compared between the control and intervention groups with student's t-tests. A multivariate analysis will be performed comparing the change in P:F ratio using linear regression, controlling for baseline P:F ratio, baseline overall disease severity (SOFA), and baseline COVID-19 related disease activity markers.

Secondary outcomes of risk for high flow nasal cannula, noninvasive ventilation, invasive ventilation will be compared between the intervention and control groups with the  $\chi^2$ -squared test. Survival to discharge will be compared with the  $\chi^2$ -squared test. Logistic regression analysis will be performed for each of these outcomes, controlling for baseline P:F ratio, baseline overall disease severity (SOFA), and baseline COVID-19 related disease activity markers.

Ventilator-free days will be compared using the student's t-test for bivariate analysis, and linear regression for multivariate analysis, controlling for baseline P:F ratio, baseline overall disease severity (SOFA), and baseline COVID-19 related disease activity markers.

Secondary outcomes of questionnaires related to subject symptoms before and after using the device will be analyzed for intra-subject change in questionnaire scores using paired student's t-tests. A multivariate analysis will be performed comparing the change in questionnaire scores using linear regression, controlling for baseline questionnaire score, baseline P:F ratio, baseline overall disease severity (SOFA), and baseline COVID-19 related disease activity markers.

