# **AirFLO2 Treatment for Hypoxia and/or Tachypnea in Patients with COVID-19**

## **Research Protocol**

**Version 3 – 21SEP2020**

**NCT04649775**

## Study Summary

Title	AirFLO2 Treatment for Hypoxia and/or Tachypnea in Patients with COVID-19
Short Title	AirFLO2 with COVID-19
IRB Protocol number	Pro00105246
Study Center	Duke
Study Aims	
Primary:  Determine if use of the AirFLO2 device will reduce hypoxia in patients admitted to the hospital with COVID-19 infection. The aim of our study is to determine whether the use of the AirFLO2 device can improve hypoxia as measured by change between baseline P:F ratio and repeat P:F ratio between 1 to 6 hours after using the device.
 
Secondary:  Determine if use of the AirFLO2 device will
 
 
a) Improve subjective symptoms related to dyspnea and comfort
 
b) reduce risk of progression to high flow nasal cannula (HFNC), non-invasive ventilation (NIV), or invasive ventilation
 
c) reduce intensive care unit (ICU) transfer risk
 
d) reduce intubation risk
 
e) reduce days of hospitalization
 
f) increase survival to discharge
 

Number of Subjects	A targeted sample size of 46 subjects will be required, with an expected dropout rate of 10%, a total sample size of 50 subjects will be necessary to complete the study.
Inclusion Criteria	
 
• Adults <math>\geq 18</math> years of age with confirmed COVID-19 infection
 
• Patient must be able to complete consent and hold mask
 
• Baseline room air oxygen saturation <math></= 94\%</math> or patient with new supplemental oxygen requirement at presentation or patient on supplemental oxygen at baseline and requiring up-titration of oxygen setting
 
 Patient must have access to an internet-connected device
Exclusion Criteria	
 
• Tracheostomy
 
• History of pneumothorax or known bullous lung disease
 
• Recent cataract surgery
 
• Patient receiving NIV (Noninvasive Ventilation) or HFNC (High Flow Nasal Cannula)
 
• Patient receiving mechanical ventilation
 
• Active TB
 
• Seizures
 

		
 
• Delirium
 
											

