#### **Study groups:**

We will enroll n=50 patients with hypoxia (O2 saturation 90% or less on RA) and use clinical data including:

- Room air oxygen saturation
- PaO2/FiO2 ratio 1 hour prior to and then 1, 2, 4, 8, 12 and every 24hours after using AirFIO2.
  - If arterial blood gas result is not available for any time point then the P:F ratio will be imputed using the SpO2.
  - If the patient is on nasal cannula, the estimated FiO2 delivery will be calculated based on the oxygen flow rate in liters per minute (LPM).
- Transition to HFNC or NIV
- ICU transfer
- Ventilator free days
- Survival to discharge
- Cardiovascular (CV) Questionnaire, Cough questionnaire, and Roth score will be completed at baseline, and before discharge by all consented participants and the two questionnaires repeated 1-6 hours after using the device for subjects randomized to receive the AirFIO2.

Additional clinical data pertaining to overall disease severity as measured by the Sequential Organ Function Assessment (SOFA) score and inflammatory markers related to COVID-19 infection will be collected:

- SOFA score
  - Platelet count

- Creatinine
- Mean arterial pressure
- Vasopressor treatment and dose
- Bilirubin
- Glasgow Coma Score (extracted from clinical documentation)
- COVID-19 inflammatory markers
  - D-dimer
  - Ferritin
  - C reactive protein (CRP)
  - Creatine kinase
  - Lymphocyte percentage

These clinical data will be obtained via chart review. For each lab value, the collection time point nearest to study enrollment will be recorded.

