### **Randomization**

After consent, subjects will be randomized to the intervention or the control group via randomization software.

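### Fifty patients less the planned 10% dropout leave 45, one below the 46 the plan requires; 50 covers at most 8% dropout

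*Combined protocol and SAP*

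**What the plan says.** The sample size paragraph of Data Analysis & Statistical Considerations gives its inputs as "assuming a hypothesized increase in P:F ratio of +25 in the intervention group, no change in P:F ratio in the control group", with a standard deviation of 30 in each group. From these it concludes that "for statistical power of 80%, a sample size of 46 subjects will be required", and adds: "With an expected dropout rate of 10%, a sample size of 50 subjects will be necessary to complete the study".

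The same figures appear in the Study Summary under Number of Subjects ("A targeted sample size of 46 subjects will be required, with an expected dropout rate of 10" percent, then a total of 50). The Study groups section uses the same enrolment number: "We will enroll n=50 patients with hypoxia".

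Two tests of the P:F ratio follow in the analysis section. The first is "The primary outcome of intra-subject change in P:F ratio before and after using the device will be analyzed with a paired student's t-test". The second is "The absolute change and percent change in P:F ratio will be compared between the control and intervention groups with student's t-tests". The Randomization section says only that "subjects will be randomized to the intervention or the control group via randomization software", with no allocation ratio. The significance level and its sidedness are not given anywhere.

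**The concern.** Two stated numbers, 46 completers needed and 10% lost, determine the enrolment figure, and 50 is not that figure. The target therefore falls short of the plan's own requirement at the plan's own dropout rate. Any reader can check this, and it is stated in two places.

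The same paragraph has a smaller gap. It attaches 80% power to a calculation without naming the test. The inputs describe a contrast between arms, yet the test named for the primary outcome is a within-subject one. What is at stake is whether the stated power is true as written and which comparison it supports.

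**Working it through.** **Inputs from the documents.** Required number 46, dropout 10%, enrolment 50; difference in change 25 − 0 = 25; SD 30 in each group; power 80%.

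**Assumed, because not stated.** Two-sided 5% level, 1:1 allocation, and 30 as the SD of the change in P:F. Steps 2 to 4 use these; step 1 does not.

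**1. The dropout step**
- Expected completers from 50: 50 × (1 − 0.10) = 45, against 46 required.
- Enrolment needed: 46 / (1 − 0.10) = 51.1. Fifty-one gives 51 × 0.90 = 45.9, still just under; 52 (26 per arm) gives 46.8.
- Largest dropout that 50 can absorb: 1 − 46/50 = 8%, which is 4 patients.
- The common shortcut of multiplying by 1.10 does not give 50 either: 46 × 1.10 = 50.6, which rounds up to 51.

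**2. Reproducing the 46**

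The normal-approximation size for two means is n per arm = 2 × [SD × (z for 0.975 + z for 0.80) / difference]².
- 2 × [30 × (1.960 + 0.842) / 25]² = 22.60, so 23 per arm and 46 in total. This matches the plan.
- A one-sided 5% level would give 18 per arm, 36 in total, so the two-sided assumption is the one that fits.
- A paired t-test with mean change 25 and SD of change 30 already has 82.2% power with 14 pairs. The 46 is therefore a between-group size and not a paired-test size.

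**3. Power at 46 and at 45 completers**

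The noncentrality is 25 / [30 × √(1/n₁ + 1/n₂)]: 2.83 for 23 and 23, and 2.79 for 23 and 22.

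| Completers | Arms | Normal approximation | Student's t-test |
|---|---|---|---|
| 45 | 23 / 22 | 79.8% | 78.0% |
| 46 | 23 / 23 | 80.7% | 78.9% |
| 47 | 24 / 23 | – | 79.8% |
| 48 | 24 / 24 | – | 80.7% |

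For the t-test the gap from 80% at 45 completers has two parts:
- from sizing with the normal approximation, 80.00 − 78.93 = 1.07 points;
- from the dropout slip, 78.93 − 77.98 = 0.95 points.

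**4. Scale**

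With 45 completers the t-test reaches exactly 80% if the SD is 29.25, and has 75.3% if the SD is 31. The whole gap is smaller than the effect of one unit in the planning SD.

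**The case against.** The strongest case on the other side is that this is rounding. The unrounded requirement is 2 × 22.60 = 45.2, so 45 completers miss it by 0.2 of a patient, and 45.2 / 0.90 = 50.2 was perhaps rounded down. By the normal approximation that appears to have produced the 46, 45 completers give 79.8%, which is 80% to the nearest percent. This stands as an account of how small the effect is. It does not make the text consistent: the plan states 46, not 45.2, and 50.2 should in any case be rounded up.

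A second objection is that restating the power as 78% does more than correct the dropout step, since about half of the drop comes from moving to the t-test, and that it writes unstated assumptions into the protocol. The split is as described in the working. The t-test figure is nevertheless the appropriate one to report, because Student's t-test is what the plan names for the between-group comparison. The assumptions are inferred and the sponsor must confirm them.

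A third is that the sizing test can be worked out from the inputs. It can, and the paired-test check supports the inference. The plan still does not say so, and it gives the primary label to the other test. The arithmetic point does not depend on this.

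Finally, one might say that intention to treat retains the dropouts. The plan gives no method for a patient with no follow-up P:F. Its SpO2-based imputation covers a missing blood gas, not a patient who has left. The plan itself treats dropout as reducing the usable number, which is why it inflates 46 at all. No replacement rule or other dropout rate appears that would rescue 50.

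**Conclusion.** The concern holds. With the plan's own three numbers and no further assumption, 50 enrolled leave 45 completers, one fewer than required, and the stated 10% dropout exceeds the 8% that 50 can absorb. The 46 is not in error; the step from 46 to 50 is.

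The consequence is minor. Assuming a two-sided 5% level, 1:1 allocation, a difference of 25 and an SD of change of 30, the slip costs about 1 point of power, and the between-group t-test stands at about 78% rather than 80%. No conclusion of the trial turns on it. It should be corrected because a stated figure contradicts its inputs in two places, and because the same sentence can settle which test the power belongs to.

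**What to change.** Replace the sample size conclusion in the Study Summary and in Data Analysis & Statistical Considerations with wording such as: *Fifty subjects, about 45 completers after 10% dropout, give about 78% power for the between-group t-test of change in P:F ratio (two-sided 5% level, 1:1 allocation, difference 25, SD of change 30).* Before adopting it, the sponsor should confirm the level, sidedness, allocation and meaning of the SD. The text should also say that this power refers to the between-group comparison and not to the paired t-test. The cost is one sentence in two places and a slightly less favourable figure. No patients are added, and the enrolment number in Study groups stays as it is.

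If the sponsor would rather change the enrolment number, there are two alternatives, each of which also changes the number in Study groups:
- **52 enrolled** (2 more) keeps the plan's 46 completers at 10% dropout (46.8 expected).
- **54 enrolled** (4 more) gives 54 × 0.90 = 48.6 expected completers; 24 per arm has 80.7% power by the t-test under the same assumptions.

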Study Schedule		
Following prescreening for eligibility, participants will provide consent. It is expected the primary consent will be performed at the in-patient bedside with a study coordinator to facilitate and answer questions.
 
After consent, baseline clinical data will be recorded and study related parameters post consent will be collected
											

Parameter	1 hr pre	baseline	1 hr	2 hr	4 hr	6 hr	8 hr	12 hr	Every 24 hr	discharge	withdraw	death
Sp02	X	X	X	X	X		X	X	X	X		X
ABG	X	X	X	X	X		X	X	X	X		X
P/F	X	X	X	X	X		X	X	X	X		X
NC L/m	X	X	X	X	X		X	X	X	X	X	X
HFNC			Yes /No	Yes /No	Yes /No		Yes /No	Yes /No	Yes /No	Yes /No	Yes /No	Yes /No
NIV			Yes /No	Yes /No	Yes /No		Yes /No	Yes /No	Yes /No	Yes /No	Yes /No	Yes /No
Ventilator free			Yes /No	Yes /No	Yes /No		Yes /No	Yes /No	Yes /No	Yes /No	Yes /No	Yes /No
Roth scale		X								X		
CV		X	(betw een	1 & 6hrs)						X		
LCQ		X	(betw een	1 & 6hrs)						X		
SOFA score		X										
Platelet		X										
Creatinine		X										
MAP		X										
Vasopressor tx		X										
Vasopressor dose		X										
Bilirubin		X										
Glasgow coma scale		X										
COVID-19 inflamm		X										

atory markers											
D-Dimer		X									
Ferritin		X									
CRP		X									
Creatine kinase		X									

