### **Design & Procedures:**

We propose an unblinded, randomized, controlled trial for use of the AirFIO2 device for patients admitted to Duke Hospital with COVID-19 and tachypnea (RR >20 breaths/min) and/or hypoxia (Oxygen saturation </=94% on room air or requiring supplemental oxygen at baseline).

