### **Intervention**

Intervention subjects will receive the AirFLO2 device and training via video with reinforcement from the coordinator how to use and to self-apply it. Bedside nurses will also be given instructions, access to the study video and verbal training as well, so that they can answer simple questions for the patients.

Initially the CRC will hand device to the patient. Oxygen saturation at baseline will be recorded. The patient will set the PEEP at 5 on the mask, then hold the mask firmly against the face, take a full slow deep breath in, then exhale steadily out until out of breath. Record oxygen saturation. Wait 3-5 minutes then repeat maneuver with PEEP at 10. Record oxygen saturation. Repeat again with PEEP at a setting of 15, then again at 20. The highest O2 saturation achieved with the lowest PEEP is the PEEP setting to use. If oxygen saturation does not change or decreases, leave at PEEP of 5.

All other elements of patient care will be managed by the treating physician(s).

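### The test labelled primary is a before-after paired t-test that ignores the control arm, and no between-arm comparison is named primary

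*Combined protocol and SAP*

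**What the plan says.** The Design & Procedures section describes an "unblinded, randomized, controlled trial" with a usual-care control group. The aim in the Study Summary, repeated under Primary objective, is the change from baseline to a "repeat P:F ratio between 1 to 6 hours after using the device". No comparator appears in that aim.

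The Data Analysis & Statistical Considerations section then contains four relevant statements:

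- Sample size: it rests on a "hypothesized increase in P:F ratio of +25 in the intervention group, no change in P:F ratio in the control group", with a standard deviation of 30 in each group, 80% power and 46 subjects (50 after dropout).
- Analysis set: "Groups will be analyzed by intention to treat", with per-protocol analyses added.
- Primary outcome: "The primary outcome of intra-subject change in P:F ratio before and after using the device will be analyzed with a paired student's t-test".
- Immediately after: "The absolute change and percent change in P:F ratio will be compared between the control and intervention groups with student's t-tests". A linear regression of the change follows, adjusted for baseline P:F, SOFA and COVID-19 activity markers.

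Neither the t-tests between arms nor the regression is called primary, and no order among the analyses is given.

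**The concern.** A paired test asks whether P:F moved in the patients tested. It cannot say whether the device moved it. Patients enter because they are hypoxic or need more oxygen, and their treating physicians manage all other care. P:F may therefore change in both arms through regression to the mean, usual care or disease progression. Randomisation deals with this, but only if the arms are compared.

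Read literally, the plan would let a significant paired test be reported as the positive primary result while the between-arm tests beside it show nothing. If patients generally worsen, the same test could miss a real benefit. Because the trial is unblinded, choosing the deciding analysis after data have been seen would be hard to defend.

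A related gap is the clock. The Study Summary, Primary objective and Study groups sections time the repeat value from use of the device, which control patients never use. The Study Schedule instead says that "baseline clinical data will be recorded and study related parameters post consent will be collected", and its hourly columns are not tied to device use. It also lists both a 1-hour-pre column and a baseline column, and P:F values at 1, 2 and 4 hours all fall inside the 1 to 6 hour window.

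**Working it through.** **Inputs from the Data Analysis & Statistical Considerations section.** Difference 25 (+25 versus 0), SD 30 in both groups, power 80%, N = 46, dropout 10%, N = 50.

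**Assumptions.** Alpha 0.05 two-sided and 1:1 allocation, neither of which is stated. SD 30 is read as the SD of the change, the natural reading of a calculation stated on the increase in P:F. The paired test is taken to be in the device arm, 23 patients.

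**1. Which test does 46 belong to?**

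- Two-sample, normal approximation: n per arm = 2 × (1.96 + 0.842)² × (30/25)² = 22.6, so 23 per arm and 46 in total. The plan's figure is reproduced.
- Paired t-test for +25 with SD 30: power is 78.8% at 13 patients and 82.2% at 14, so 14 patients are needed.

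The sample size was therefore built for the between-arm comparison. With the t distribution, between-arm power is 78.9% at 23 per arm and 78.0% with 45 evaluable (50 less 10%).

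**2. What makes each test significant at SD 30?**

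- Paired, n = 23: t(0.975, 22) × 30/√23 = a mean rise of 13.0.
- Between arms, 23 per arm: t(0.975, 44) × 30 × √(2/23) = a difference of 17.8.

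**3. No device effect, same rise in both arms.** The documents give no estimate of a common change, so the drifts below are assumptions. The paired column is from the noncentral t; the other two are from 200,000 simulated trials with 23 per arm.

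| Common rise (P:F units) | Paired test significant | Between-arm test significant | Paired significant, between-arm not |
|---|---|---|---|
| 5 | 12% | 5% | 10% |
| 10 | 33% | 5% | 31% |
| 15 | 63% | 5% | 60% |
| 25 | 97% | 5% | 93% |

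**4. True device effect of +25, same decline in both arms.**

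- Decline of 10: the device arm rises 25 − 10 = 15, and paired power is 63%.
- Decline of 15: the device arm rises 25 − 15 = 10, and paired power is 33%.
- Between arms the decline cancels, and power stays at 79%.

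**The case against.** The strongest reply is that the sentence should be read with its paragraph. The between-arm t-tests come next, concern the same endpoint and precede the secondary outcomes. Together with the randomised design, intention to treat and the sample size, they suggest that the authors meant to compare arms. On this view every needed comparison is planned and the fault is a misplaced label. It is true that nothing is missing from the list of analyses, and that the plan states no success rule for any test. But the only analysis tied to the words primary outcome is the paired one, and elsewhere in the same section the plan says explicitly when it means a comparison between groups. A reader should not have to infer the deciding test from the sample size.

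The drifts are also open to challenge. The plan expects no change in controls. A common shift of 25 within hours would equal the whole hypothesised effect, and at a drift of 2 units the paired test rejects in only about 6% of trials. A baseline taken after consent would also lessen regression to the mean, though not drift under usual care. This stands: the table shows how sensitive the paired test is and does not predict what will happen.

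Finally, the smallest repair would be to name the planned t-test on absolute change as primary. A regression on arm and baseline P:F alone is a reduced form of the planned model, and the 79% and 78% power figures are for the t-test. Both points are correct. Either choice would cure the defect.

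**Conclusion.** The concern holds, and the plan should be changed before analysis. The test labelled primary does not answer the randomised question, and no analysis that does is designated primary. That conclusion rests on the text and on the sample size, which reproduces as a two-sample calculation (46) and not as a paired one (14).

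The size of the possible error depends on an unknown common change in P:F. For assumed rises of 5 to 25 units, the false-positive rate of the paired test runs from 12% to 97%; for assumed declines of 10 to 15 units, its power falls to between 63% and 33%. These figures assume SD 30 for the change, 23 patients per arm and two-sided 0.05. The unclear time zero and choice of values are secondary points to reconcile; they do not prevent an intention-to-treat comparison.

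**What to change.** Replace the paired-test sentence with wording such as:

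> The primary analysis compares change in P:F ratio between the randomised arms by intention to treat, using linear regression of the change on arm and baseline P:F, at a two-sided alpha of 0.05. Within-arm paired t-tests are descriptive. The between-arm t-tests on absolute and percent change, and the regression that also includes SOFA and disease activity markers, are supportive.

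Naming the already planned between-arm t-test on absolute change as primary is an acceptable alternative.

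Then reconcile the timing from device use (Study Summary, Primary objective, Study groups) with the Study Schedule. State one time zero that applies to both arms, which column is the baseline (1 hour pre or baseline), and which single scheduled value (1, 2 or 4 hours) is the repeat value.

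The cost is small. Naming the primary test is a change of wording and uses variables already in the planned regression. The timing points are decisions for the study team to write down, and the P:F values are already scheduled. The sample size need not change materially: between-arm t-test power is 79% at 46 evaluable and 78% at 45.

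### The adjusted logistic models carry too many covariates for 50 patients: the odds ratios will be very imprecise and, if events are rare, may not exist

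*Combined protocol and SAP*

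**What the plan says.** Data Analysis & Statistical Considerations plans four binary secondary outcomes: high flow nasal cannula (HFNC), non-invasive ventilation (NIV), invasive ventilation and survival to discharge. Each gets an unadjusted chi-squared test; for survival, for example, "Survival to discharge will be compared with the" chi-squared test. Each then gets an adjusted model: "Logistic regression analysis will be performed for each of these outcomes, controlling for baseline P:F ratio, baseline overall disease severity (SOFA") and, as a third item, "baseline COVID-19 related disease activity markers".

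The markers are named only as a group. The list under Study groups has five: D-dimer, ferritin, C reactive protein, creatine kinase and, last, "Lymphocyte percentage". The parameter table in the Study Summary has four, ending at "Creatine kinase" with no lymphocyte row. No section says which markers enter, whether they are combined or transformed, what event rates are expected, or what happens if events are sparse or a model cannot be fitted.

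The sample size rests on P:F change alone. Randomization says that "subjects will be randomized to the intervention or the control group via randomization software" and gives no allocation ratio.

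**The concern.** A logistic model draws its information mainly from the rarer outcome category, not from the total number of patients. With 50 patients and up to seven covariates beside treatment arm, that category is thin for every slope. There are two consequences. Where the estimate exists, it is imprecise and often exaggerated. Where events are few, some combination of arm and covariates may separate events from non-events exactly, and maximum likelihood then has no finite odds ratio.

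At stake are the adjusted results for the outcomes that matter most to patients. An odds ratio far from 1 with a huge interval is easily misread, and some of the four models may give nothing to report. The problem is not false claims of benefit, because the Wald test does not reject materially too often.

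**Working it through.** **The plan's own figure.** The effect is set by "assuming a hypothesized increase in P:F ratio of +25 in the intervention group, no change in P:F ratio in the control group"; the SD of the change is taken as 30 per arm, with 80% power. Two-sided alpha 0.05 and 1:1 allocation are not stated and are assumed.

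n per arm = 2 × (1.960 + 0.842)² × 30² / 25² = 22.6, rounded up to 23, so 46 in total.

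This reproduces the plan's 46, with 50 to be enrolled. Nothing in it concerns the binary outcomes.

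**Events per slope.** Assume one linear term per marker.

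- Slopes: arm + P:F + SOFA + 4 markers = 7, or + 5 markers = 8.
- The rarer category holds at most 50/2 = 25 patients.
- Maximum events per slope: 25/7 = 3.6, or 25/8 = 3.1. This needs no event rate.
- At assumed rates with 8 slopes: 50 × 0.10/8 = 0.6; 50 × 0.20/8 = 1.25; 50 × 0.30/8 = 1.9.
- If 10% drop out, 45 remain and the ceiling with 8 slopes is 22.5/8 = 2.8.

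**Simulation.** There were 2,400 trials per cell, each with 25 patients per arm (assumed), no device effect, and seven standard normal covariates with log odds ratio 0.3 each. Covariate correlation was 0 or 0.4, which gives the two ends of each range. Models were fitted by ordinary maximum likelihood unless stated, and separation was detected by linear programming. Monte Carlo standard error is at most about 1.3 points. Event rates are assumed. "Beyond 5-fold" means an odds ratio above 5 or below 1/5 when the truth is 1; those rows all use the trials in which the 8-slope estimate exists.

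| % of trials, by event rate | 10% | 13% | 20% | 30% | 50% |
|---|---|---|---|---|---|
| No finite odds ratio, 8 slopes | 30.9-44.7 | 15.9-28.0 | 3.2-10.0 | 0.2-1.7 | 0.0-0.2 |
| No finite odds ratio, 7 slopes | 23.8-35.2 | 11.3-21.2 | 1.6-6.1 | 0.0-0.8 | 0.0-0.2 |
| An arm with no events (exact) | 13.8 | 6.1 | 0.8 | 0.0 | 0.0 |
| Beyond 5-fold, 8 slopes | 34.4-39.0 | 26.7-32.6 | 18.1-26.0 | 10.0-17.5 | 6.8-11.6 |
| Beyond 5-fold, arm + P:F + SOFA | 10.8-12.4 | 8.9-11.1 | 6.2-8.1 | 2.5-5.3 | 1.3-2.7 |
| Beyond 5-fold, same three terms, Firth | 3.3-4.0 | 2.9-4.5 | 3.6-4.2 | 1.3-3.1 | 0.6-1.4 |
| Beyond 5-fold, unadjusted | 5.7 | 5.6-6.1 | 4.1-4.5 | 1.5-1.6 | 0.7 |
| Wald false positives, 8 slopes | 0.5-1.5 | 1.7-1.9 | 2.8-4.2 | 4.9-5.5 | 5.9-6.1 |

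The empty-arm row is 1 − [1 − (1 − p)²⁵]². At 10%, 0.9²⁵ = 0.0718 and the result is 0.138. That share of the failures also defeats an unadjusted odds ratio; the rest comes from the covariates.

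**Interval width at 20% events.** The median ratio of upper to lower 95% limit is about 48 to 88 with 8 slopes, against 21 to 27 with arm, P:F and SOFA.

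**What the upper ends mean.** Correlated covariates with the same coefficients are jointly more prognostic. With correlation 0.4 and the log odds ratio cut to 0.163, so that total prognostic strength equals the independent case, the 8-slope model has no estimate in 31.8/15.1/2.5/0.1/0.0% and is beyond 5-fold in 32.4/28.4/20.8/9.9/6.6%. The upper ends therefore reflect stronger prognosis, not correlation itself.

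**Different assumptions.** A second simulation used correlation 0.3, log odds ratio 0.4 for P:F and SOFA and 0.2 per marker, and 1,000 trials per scenario.

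- No finite estimate with 8 slopes: 35% of trials at 10% events, 5% at 20%, under 1% from 30% up.
- Dropping the markers changes the median limit ratio from 353 to 70 at 10% events, 63 to 23 at 20%, 31 to 15 at 30% and 22 to 12 at 50%.
- With 45 evaluable patients, non-existence is 45% at 10% events and 11% at 20%.
- With a true odds ratio of 0.4, it is 61% and 16% at baseline rates of 10% and 20%.

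**The case against.** **The covariate count is an assumption.** The wording would also fit one selected marker or a score. That is so, and 7 or 8 slopes is a reading. But the plan contains no reduction rule, and if the choice is left open it would be made after the data are seen. Prespecifying a small model answers both readings.

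**No event rate is given, so rarity is unproven.** This stands for non-existence, which is negligible from 30% events up. It does not stand for imprecision: at 50% events, the most favourable case, the 8-slope estimate is beyond 5-fold in 6.8-11.6% of trials, against 0.7% unadjusted. The objectives could be read as one composite of HFNC, NIV or invasive ventilation, with more events, but the analysis text asks for a model for each outcome.

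**Much of the imprecision is simply 50 patients.** This is partly right. Ratios of limits look dramatic because they are exponentiated. On the log scale at 20% events, standard error = ln(ratio)/3.92: ln(48)/3.92 = 0.99 to ln(88)/3.92 = 1.14 with 8 slopes, and 0.78 to 0.84 with arm, P:F and SOFA. The marker block adds roughly a quarter to a third. The smaller model is still imprecise, but the added part is avoidable.

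**The evidence does not cover the recommended method.** The 21- to 27-fold width is for ordinary maximum likelihood, and no width is available for the Firth profile interval. However, the penalised likelihood-ratio test rejects in 3.2-5.2% of null trials, so its interval covers the true value of 1 in 94.8-96.8%. Shrinkage is favoured when the truth is no effect, but a check at a true odds ratio of 0.4 also gave the reduced Firth model much lower error than the planned one.

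**These are secondary analyses with chi-squared tests beside them.** This is true, and it limits the weight of the point. Those tests do not depend on the number of covariates, although their approximation is itself doubtful below about 10 events in total (probability 97.5/89.3/44.4/4.0/0.0% at the five assumed rates).

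**Conclusion.** The concern holds. If each marker enters as one linear term, the planned models have at most 3.1 to 3.6 events per slope whatever the event rate. The adjusted odds ratios will then be very imprecise and exaggerated more often than necessary. Non-existence is a real risk at about 10-20% events and a negligible one from 30% up.

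The ceiling on events per slope follows from 50 patients and the two marker lists. The percentages rest on assumed event rates, 25 patients per arm, no device effect, assumed covariate effects and ordinary maximum likelihood. They should be read as orders of magnitude, with the lower ends nearer the case of independent or moderately prognostic covariates.

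The fault is confined to the adjusted secondary binary analyses. It does not inflate false positives materially and does not touch the primary P:F comparison. It should be changed, but it does not threaten the trial's main conclusion.

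**What to change.** In Data Analysis & Statistical Considerations, limit each of the four logistic models to arm, baseline P:F ratio and at most SOFA, and leave out the individual markers. Fit by Firth penalised likelihood, whose estimate stays finite under separation, with profile-penalised confidence intervals. Report the unadjusted risk difference beside it, with a score or exact interval.

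Both parts contribute. At 20% events, cutting the covariates alone takes estimates beyond 5-fold from 18.1-26.0% to 6.2-8.1%; adding Firth takes them to 3.6-4.2%.

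If marker adjustment is wanted, one prespecified composite marker score as a single extra term is acceptable. With Firth and the mean of five standardised markers, 4.2-5.1% are beyond 5-fold at 20% events. The composite would need a stated marker list, so the four-row table and the five-item list should be reconciled.

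The cost is analysis wording only. What is lost is adjustment for individual markers in these secondary outcomes, which is minor because randomisation already makes the unadjusted comparison valid. No change to the primary analysis or its linear model is proposed.
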